Under NRI, all nonresponders at Week 16 (Visit 8), as well as all patients who discontinue study treatment at any time prior to Week 16 for any reason, will be defined as nonresponders for the NRI analysis at Week 16. NRI will be applied to Week 52 (Visit 15) in a similar method. Patients who are deemed as inadequate responders by the investigator after Week 16 but remain on blinded study treatment and only have modifications in concomitant medications will not be automatically imputed as nonresponders. However, patients who discontinue originally assigned blinded study treatment and use rescue ixekizumab 80 mg Q2W will be analyzed as nonresponders for the Week 52 analysis. Randomized patients without any postbaseline observation will also be defined as nonresponders for the NRI analysis.

A multiple testing strategy for the primary and major secondary objectives will be implemented to control the family-wise type I error rate at a 2-sided  $\alpha$  level of 0.05.

The primary analyses for the continuous efficacy and health outcomes variables will be made using mixed-effects model of repeated measures (MMRM) analysis with treatment, geographic region, screening MRI/CRP status, baseline value, visit, baseline value-by-visit, and treatment-by-visit interactions as fixed factors.

A secondary analysis for continuous efficacy and health outcomes variables will be made using analysis of covariance (ANCOVA) with treatment, geographic region, screening MRI/CRP status, and baseline.

Fisher's exact test will be used for all adverse events (AEs), baseline, discontinuation, and other categorical safety data. Continuous vital sign and laboratory values will be analyzed by an ANCOVA with treatment and baseline value.

Patients who discontinue study treatment after Week 16 will continue to be followed for all regularly scheduled visits for safety and efficacy assessment. The data collected after discontinuation of study treatment will be summarized separately.

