## 4. Study Design

### 4.1. Overview of Study Design

Study IIF-MC-RHBX (RHBX) is a Phase 3, multicenter, randomized, double-blind, placebo-controlled, parallel-group, outpatient study examining the efficacy and safety of 2 ixekizumab treatment regimens (80 mg Q2W and 80 mg Q4W SC) as compared to placebo SC in patients with active nonrad-axSpA who are bDMARD-naïve, during a double-blind, 52-week treatment period (Period 2).

[Figure RHBX.1](#) illustrates the study design. Within the active treatment groups, half the patients will be given a 160-mg starting dose and the other half will be given an 80-mg starting dose. All treatment groups and administration of the investigational product are described in [Section 6.1](#), and the Study Drug Administration Log is described in [Section 6.2.1](#).

All procedures to be conducted during the study, including timing of all procedures, are indicated in the Schedule of Activities ([Appendix 2](#)). Selected study procedures are to be performed before administration of the investigational product, as applicable.

For each patient, x-rays and magnetic resonance imaging (MRIs) will be collected according to [Section 8.1.2.21.1](#) and the Schedule of Activities ([Appendix 2](#)).

[Appendix 3](#) lists the specific laboratory tests that will be performed for this study. At or after Week 16, patients who are deemed inadequate responders may receive rescue therapies as described in [Section 6.1.1](#). Patients discontinuing study treatment after Week 16 are to remain in the study and follow the regular visit schedule.

[figure not shown]
Patients who have taken at least 1 study dose and who discontinue study treatment prior to Week 16 or study participation (regardless of timing) are to complete an early termination visit (ETV) and enter into post-study follow-up for at least 12 weeks after the ETV date or the last regularly scheduled visit. Patients whose ETV or last regularly scheduled visit is longer than 12 weeks after their last investigational study medication dose are not required to enter into the Post-Study Follow-Up Period (Period 3). For the management of patient safety, patients are to be monitored through the Post-Study Follow-Up Period as indicated on the Schedule of Activities ([Appendix 2](#)).

Patients who complete Study RHBX may be eligible to enroll into a long-term extension study (Study IIF-MC-RHBY [RHBY]) for up to 2 additional years.

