When the MMRM is used, the model will include treatment, geographic region, screening MRI/CRP status, baseline value, visit, baseline value-by-visit, and treatment-by-visit interaction as fixed factors. The covariance structure to model the within-patient errors will be unstructured. If the unstructured covariance matrix results in a lack of convergence, the similar approach specified above for categorical MMRM will be used. The Kenward-Roger method will be used to estimate the denominator degrees of freedom. Type III tests for the least-squares (LS) means will be used for the statistical comparison; the 95% CI will also be reported. Treatment group comparisons with placebo at Week 16 (Visit 8), Week 52 (Visit 15), and all other visits will be tested.

When the ANCOVA is used, the model will include treatment, geographic region, screening MRI/CRP status and baseline value. Type III sums of squares for the LS means will be used for the statistical comparison; the 95% CI will also be reported.

The impact of ixekizumab starting dose of 160 mg versus 80 mg on time to onset (focusing on Week 4) and treatment response during Blinded Treatment Dosing Period will be summarized and evaluated. Details will be specified in the SAP.

For variables that are not collected at each postbaseline visit, data may exist at visits where the variable was not scheduled to be collected due to early discontinuation visits. In these situations,

data from the early discontinuation visit that does not correspond to the planned collection schedule will be excluded from the MMRM and Categorical MMRM analyses. However, the data will still be used in other analyses, including shift analyses, change from baseline to last-observation carried forward (LOCF) or modified baseline observation carried forward (mBOCF) endpoint analyses, and other categorical analyses.

Fisher's exact test will be used for all AE, baseline, discontinuation, and other categorical safety data. Continuous vital sign and laboratory values will be analyzed by an ANCOVA with treatment and baseline value in the model.

Patients who discontinue study treatment after Week 16 will continue to be followed for the scheduled visits for safety and efficacy assessment. The data collected post discontinuation of study treatment will be summarized separately.

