## **9.5. Safety Analyses**

Safety will be assessed by summarizing and analyzing AEs including adjudicated cerebrocardiovascular events, laboratory analytes including neutrophil counts, QIDS-SR16, C-SSRS, and vital signs. The duration of treatment exposure will also be summarized.

For Period 2 (Blinded Treatment Dosing Period), safety data will be summarized for the safety population. Treatment group comparisons on categorical safety data will be performed using Fisher's exact test as described in Section 9.2.1. Continuous safety data will be analyzed by an ANCOVA model as described in Section 9.2.1.

For patients who are deemed as inadequate responders by investigators after Week 16 and for whom the investigator indicates the need for modified treatment by the use of rescue ixekizumab 80 mg Q2W, safety data collected after initiation of modified treatment by ixekizumab 80 mg Q2W will be summarized separately.

Safety data collected after study treatment discontinuation will be summarized separately.

For post-study follow-up (Period 3), safety data will be summarized according to the treatment patients were on prior to entering the Post-Study Follow-Up Period.

The categorical safety measures will be summarized with incidence rates. The mean change of the continuous safety measures will be summarized by visits.

Further details will be described in the SAP.

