## **6.1.2. General Considerations for Analyses during the Blinded Treatment Dosing Period (Period 2)**

### **6.1.2.1. Intent-to-Treat Population and Safety Population**

Period 2 starts at the first injection of study treatment at Week 0 (Visit 2) and ends on the date of Week 52 (Visit 15) or the early termination visit (ETV; between Weeks 0 and 52). For patients who were deemed as inadequate responders by their investigators and were treated with biologic rescue of ixekizumab 80 mg Q2W, only data up to the time of initiation of biologic rescue of ixekizumab 80 mg Q2W will be included in the Period 2 analyses using the ITT and Safety Populations. These patients will be considered nonresponders to categorical assessment per the nonresponder imputation (NRI) method after initiation of biologic rescue with ixekizumab 80 mg Q2W. Data collected after biologic rescue therapy has started will be summarized separately for the IR Population (Section 6.1.2.2).

Baseline for ITT and Safety Populations will be defined as the last available value before the first injection for efficacy, health outcomes, and safety analyses. In most cases, this will be the measure recorded at Week 0 (Visit 2). For efficacy measures, if the patient does not take any injection, the last available value on or prior to randomization date will be used. Change from baseline (CFB) will be calculated as the visit value of interest minus the baseline value. For safety analyses using a baseline period, the baseline period is defined as the time from Visit 1 to the date/time of the first injection.

Comparisons between each initially randomized ixekizumab treatment group (80 mg Q2W or 80 mg Q4W) and initially randomized placebo will be performed for all analyses in Period 2.

The randomization to treatment groups is stratified by country and screening MRI/CRP status (positive MRI and elevated CRP; positive MRI and nonelevated CRP; negative MRI and elevated CRP) as described in Protocol Section 6.2. The countries will be categorized into geographic regions for analysis. Geographic regions are defined in Table RHBX.6.3. Unless otherwise specified, the statistical analysis models will adjust for geographic region and screening MRI/CRP status.

Screening MRI and CRP status included in all the analysis models for Period 2 is determined based on the MRI readings and central lab CRP values obtained at screening visit (Visit 1).

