### **6.3.2. Modified Baseline Observation Carried Forward**

An mBOCF analysis will be performed on continuous efficacy and health outcomes variables in the major and other secondary objectives. For ITT population, if patients did not initiate the rescue ixekizumab 80 mg Q2W and discontinue study drug due to an AE, the baseline observation will be carried forward to the corresponding time point for evaluation; if they discontinue study drug for any other reason, the last nonmissing observation before study drug discontinuation will be carried forward to the corresponding time point for evaluation. For ITT patients who discontinue originally assigned blinded study treatment and initiate biologic rescue of ixekizumab 80 mg Q2W (inadequate responders), the last nonmissing observations prior to the initiation of rescue ixekizumab 80 mg Q2W will be carried forward to subsequent time points. Randomized patients without at least 1 postbaseline observation will not be included for evaluation with the exception of patients discontinuing study treatment because of an AE.

For IR population during the biologic rescue of ixekizumab period, if patients discontinue study drug due to an AE, the baseline observation at Week 0 will be carried forward to subsequent time points; if they discontinue study drug for any other reason, the last nonmissing observation will be carried forward to the corresponding time point for evaluation.

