### **6.10.2. Major Secondary Efficacy Analyses**

The major secondary outcomes at Week 16 (Visit 8) are:

- Proportion of patients achieving ASAS40 response at Week 16 (for regulatory agencies that require Week 52 as primary endpoint)
- Change from baseline in ASDAS at Week 16
- Change from baseline in SF-36 PCS at Week 16
- Proportion of patients achieving ASDAS low disease activity (<2.1) at Week 16
- Change from baseline in BASDAI at Week 16
- Change from baseline in MRI of the SIJ [SPARCC score] at Week 16

The major secondary outcomes at Week 52 (Visit 15) are:

- Change from baseline in ASDAS at Week 52
- Change from baseline in SF-36 PCS at Week 52
- Proportion of patients achieving ASDAS low disease activity (<2.1) at Week 52
- Change from baseline in BASDAI at Week 52

The major secondary analysis will be based on the ITT Population for Period 2 comparing each ixekizumab treatment group and placebo at Week 16 and/or Week 52 as appropriate. In the major secondary analyses, treatment groups of ixekizumab 80 mg Q2W and Q4W will be analyzed without regard to starting dose.

The primary analysis for categorical major secondary outcomes is a logistic regression analysis with treatment, geographic region, and screening MRI/CRP status in the model (Section 6.1.2). For inadequate responders who were treated with biologic rescue of ixekizumab 80 mg Q2W, only data up to the time of initiation of biologic rescue of ixekizumab 80 mg Q2W will be included in the primary analysis. These patients will be considered nonresponders to categorical assessment per the NRI imputation method (Section 6.3.1) after initiation of biologic rescue with ixekizumab 80 mg Q2W.

The primary analysis for continuous major secondary outcomes (except MRI of SIJ SPARCC score) is an MMRM analysis with treatment, geographic region, screening MRI/CRP status, baseline value, visit, baseline value-by-visit, and treatment-by-visit interaction as fixed factors (Section 6.1.2). Data after initiation of biologic rescue of ixekizumab 80 mg Q2W will not be included in MMRM analyses.

The primary analysis for change from baseline in MRI of SIJ SPARCC score at Week 16 is an observed case analysis using ANCOVA with treatment, geographic region, screening MRI/CRP status and baseline value in the model (Section 6.1.2). Only patients with both baseline and Week 16 MRI of SIJ SPARCC score will be included in the analysis.

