### 6.13.1. Extent of Exposure

Duration of exposure to study drug will be summarized by treatment group for the Safety Population and IR Population during Period 2 using descriptive statistics.

A by-patient listing of exposure duration with number of active injections and total dose will be provided.

The duration of exposure on initially assigned treatment for the Safety Population will be calculated as:

*Date of last visit on initially assigned treatment (scheduled or unscheduled) or the first date of biologic rescue in Period 2 (for inadequate responders) – Date of first dose in Period 2+1*

Note that patients who are inadequate responders and therefore rescued by ixekizumab 80 mg Q2W during Period 2 will only have their exposure calculated up until the date of rescue.

The duration of ixekizumab exposure for IR Population will be calculated as:

*Date of last visit (scheduled or unscheduled) on or prior to ixekizumab treatment discontinuation in Period 2 –  
Date of first injection of biologic rescue of ixekizumab 80 mg Q2W+1*

The number and percentage of patients in the following categories will be included in the summaries as appropriate:

- >0, ≥7 days, ≥14 days, ≥30 days, ≥60 days, ≥90 days, ≥120 days, ≥150 days, ≥183 days, ≥210 days, ≥273 days and ≥365days. Note that patients may be included in more than 1 category.
- >0 to <7 days, ≥7 to <14 days, ≥14 to <30 days, ≥30 to <60 days, ≥60 to <90 days, ≥90 to <120 days, ≥120 to <150 days, ≥150 to <183 days, ≥183 to <210 days, ≥210 to <273 days, ≥273 to <365 days and ≥365 days.

The summaries will also include the following information:

- Total exposure in patient years, calculated as:

$$\text{Total exposure in patient years} = \frac{\text{Sum of duration of exposures for all patients in treatment group}}{365.25}$$

- Mean and median total dose. Total dose (in mg) is calculated by the number of active injections taken during the treatment period multiplied by dose.
  - For those randomized to ixekizumab 80 mg (Q2W or Q4W), the total dose (in mg) taken during Period 2 prior to biologic rescue of ixekizumab 80 mg Q2W will be calculated as:

*Total number of active injections (including loading doses, if any) received in Period 2 before biologic rescue of ixekizumab 80 mg Q2W x 80*

- For those patients receiving biologic rescue ixekizumab 80 mg Q2W, the total dose (in mg) on rescue ixekizumab will be calculated as:

*Total number of injections of biologic rescue of ixekizumab 80 mg Q2W x 80.*

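### The SAP states no cut at treatment discontinuation for the Week 52 MMRM or the Period 2 TEAE tables, although the protocol says later data are summarised separately

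*SAP*

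**What the plan says.** **Follow-up.** Off-treatment data will exist. Protocol 4.1: "Patients discontinuing study treatment after Week 16 are to remain in the study and follow the regular visit schedule".

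**Protocol rule.** Section 9.2.1, directly after noting that safety and efficacy assessments continue in these patients, says: "The data collected post discontinuation of study treatment will be summarized separately". The synopsis says the same: "The data collected after discontinuation of study treatment will be summarized separately". Section 9.5 repeats it for safety: "Safety data collected after study treatment discontinuation will be summarized separately".

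**SAP rule.** For the ITT and Safety Populations, SAP 6.1.2.1 says Period 2 "ends on the date of Week 52 (Visit 15) or the early termination visit". The only data cut it states is the start of ixekizumab rescue. SAP 6.10.2 applies that cut to the continuous endpoints: "Data after initiation of biologic rescue of ixekizumab 80 mg Q2W will not be included in MMRM analyses". SAP 6.10.3 repeats it for the categorical MMRM, and 6.13 and 6.13.2 repeat it for the Safety Population tables.

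**Event and exposure windows.** Under SAP 6.13.2 an event can be treatment-emergent up to the last visit of the treatment period. Under SAP 6.13.1, exposure in the same population runs to "Date of last visit on initially assigned treatment (scheduled or unscheduled) or the first date of biologic rescue in Period 2".

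**Where stopping is handled.** NRI (SAP 6.3.1) makes a patient who stops a nonresponder. Under mBOCF (SAP 6.3.2), after a stop for reasons other than an AE, "the last nonmissing observation before study drug discontinuation will be carried forward to the corresponding time point"; after an AE the baseline value is used. The rescue period of the Inadequate Responder Population (SAP 6.1.2.2) ends at treatment discontinuation or at the start of another biologic.

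**The concern.** Protocol 9.2.1 gives its reason for cutting data at rescue: benefit from a modified treatment should not be credited to the randomised one. Values recorded after a patient has stopped treatment raise a similar problem, and the protocol sets them aside too. The SAP carries over the first cut but not the second. Its revision history records no decision to drop it.

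On efficacy, the exposed confirmatory endpoints are the Week 52 changes in ASDAS, BASDAI and SF-36 PCS, all in the Week 52 testing list of SAP 6.5.2. No other drug is needed for an effect. An ixekizumab patient who stops, drifts back towards placebo and keeps attending pulls the ixekizumab mean towards the placebo mean.

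On safety, events that start after treatment has stopped would be counted with on-treatment events in the whole-Period-2 tables. In the exposure-adjusted rates they would also be counted without matching person-time.

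**Working it through.** The plan states no figure on this point, so there is none to reproduce. The check compares texts and adds two illustrations.

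**Step 1: which patients.** Those who stop before Week 16 go to an early termination visit, which ends Period 2. Those who take ixekizumab rescue are cut at rescue. That leaves patients who stop after Week 16, are never rescued and keep attending.

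**Step 2: which rule applies to their later data.**

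| Analysis | Stated cut at rescue | Stated handling of a stop without rescue |
|---|---|---|
| NRI (SAP 6.3.1) | Yes | Yes: nonresponder |
| mBOCF ANCOVA (SAP 6.3.2) | Yes | Yes: last value before the stop, or baseline after an AE |
| MMRM (SAP 6.10.2) | Yes | None |
| Categorical MMRM (SAP 6.10.3) | Yes | None |
| ASDAS tipping point (SAP 6.3.5) | Yes: all observed data up to rescue are used | None for values observed after the stop |
| TEAE tables, Safety Population (SAP 6.13, 6.13.2) | Yes | None |
| Exposure, Safety Population (SAP 6.13.1) | Yes | Yes: last visit on initially assigned treatment |
| Separate summary promised in Protocol 9.2.1 and 9.5 | Yes, for the Inadequate Responder Population | None planned |

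Period 2 runs to Week 52 and nothing removes these values, so a programmer following the SAP would keep them.

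**Step 3: illustrative effect on a Week 52 mean difference.** Let q be the share of each arm's observed Week 52 values that come from patients off treatment. Let D_on and D_off be the between-arm differences on and off treatment.

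D_obs = (1 − q) × D_on + q × D_off

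Assume D_off = 0, that is, equal off-treatment outcomes. The documents give no q.

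- q = 5%: D_obs = 0.95 × D_on
- q = 10%: D_obs = 0.90 × D_on
- q = 20%: D_obs = 0.80 × D_on

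The denominator of q excludes rescued patients. If a share s of the arm stops and a share r is rescued, q = s/(1 − r). For example, s = 5% and r = 50% (assumed) give q = 10%. The formula treats the MMRM as a difference of observed means, which is a simplification.

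**Step 4: illustrative event and exposure mismatch.** Assume no rescue and a mean stop at Week 34, the midpoint of Weeks 16 and 52. Let q now be the share of the arm that stops.

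Event window / exposure = 52 / [(1 − q) × 52 + q × 34]

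- q = 5%: 52/51.1 = 1.018
- q = 10%: 52/50.2 = 1.036
- q = 20%: 52/48.4 = 1.074

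Under these assumptions the event window exceeds the person-time by about 2-7%.

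**The case against.** **No sentence tells the analyst to include these data.** True. Inclusion follows from the Period 2 definition and the lack of an exclusion; the tipping-point text comes closest to an instruction. The de-jure label on the categorical MMRM and the end of the exposure window point to an on-treatment intent. That intent is still not written as a data rule.

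**The tension is already in Protocol 9.2.1.** That section also ends Period 2 at Week 52 or early termination, and it uses explicit only-data-before wording for rescue alone. This is fair. But Protocol 9.5 uses the same separate-summary phrase for data after rescue, which are kept out of the main tables. Even if the phrase means only an extra summary, the SAP does not plan one.

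**Keeping off-treatment data can be a legitimate treatment-policy choice, and dilution is conservative for superiority.** Both stand. The choice would have to be stated and justified, because it departs from the protocol.

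**Stronger readings that the documents do not support.**

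- A reader might infer that never-rescued placebo patients will be on a TNF inhibitor at Week 52. The TNF-inhibitor paragraph of Protocol 6.8 bars these drugs only until study medication and/or rescue is discontinued. The general text of 6.8 allows previously excluded axSpA agents only after entry to Period 3. The described TNF-inhibitor route (Protocol 6.1) follows failed ixekizumab rescue, and those patients are already cut. The other-biologic group in SAP Table RHBX.6.2 fits them equally well, and the SAP revision history dropped the analyses of other biologics after rescue because too few patients took them.
- A reader might reach a 50% dilution by assuming that 15% of placebo patients stop, half the arm is rescued, off-treatment gain is 1.0 ASDAS unit and the true difference is 0.6: (0.15/0.5) × 1.0 = 0.30, and 0.30/0.6 = 50%. None of these inputs is in the documents, and the sum ignores the earlier visits of rescued patients that the MMRM uses.
- A reader might see the MMRM and mBOCF analyses as contradictory. A primary and a secondary analysis may differ by design; the comparison shows only that stopping is handled in one and not in the other.

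**Conclusion.** The point holds, within limits. For never-rescued patients who stop after Week 16, the SAP's data rule departs from Protocol 9.2.1 and 9.5, and the promised separate summary is missing. This is more than absent detail: followed as written, the SAP gives a result that the protocol rules out.

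Within the confirmatory family, only the Week 52 MMRM endpoints (ASDAS, BASDAI, SF-36 PCS) are affected. The supportive categorical MMRM at Week 52 shares the gap. The primary ASAS40 analysis and ASDAS below 2.1 use NRI, and Week 16 results precede the data at issue, so both are essentially unaffected. On safety, the whole-Period-2 tables are affected and the Week 0-16 tables essentially are not. The mismatch of windows concerns only the exposure-adjusted rates, not the crude percentages.

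The likely direction is dilution of the Week 52 difference. Its size cannot be estimated from the documents. The 5-20% range assumes 5-20% of observed values off treatment in each arm and equal off-treatment outcomes.

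**What to change.** 1. **SAP 6.1.2.1 and 6.10.2.** State that values recorded after permanent discontinuation of the originally assigned treatment are excluded from the MMRM, whether or not rescue was used, and are summarised separately as the protocol says. Carry the same sentence into 6.10.3, 6.3.4 and 6.3.5 so that the supportive and sensitivity analyses use the same data. If the sponsor prefers to keep these values, the departure from the protocol should be documented and justified.
2. **SAP 6.13.1 and 6.13.2.** Define one common end date for events and person-time in the exposure-adjusted rates. Report later events in the separate summary, so that no safety data are lost. Cutting every TEAE table at the last on-treatment visit is not advised: it could remove events soon after the last dose from the comparative tables, and Protocol 6.1 gives a half-life of about 13 days.
3. **Protocol 6.8.** The general text and the TNF-inhibitor paragraph on other therapy after discontinuation must be reconciled. Which of them is right is for the sponsor to decide.

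The cost is SAP wording, a derived discontinuation date in the analysis data sets, one additional set of summaries and a protocol clarification. No new data are needed.
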